We therefore propose a randomized, double blind, RCT to address the following aim:  
To determine the relative efficacy and safety of IV lidocaine among patients with acute abdominal pain, when compared to IV hydromorphone, the putative standard of care

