### Measures

- 1) Pain intensity will be measured using a verbal numerical scale of which 0 represents no pain and 10 represents the worst pain imaginable
- 2) Medication preference. Preference for a specific medication is a highly patient centered outcome, in which an individual determines for herself the benefit of a particular drug versus the adverse effects experienced. We will include in this study a measure that has been used in multiple ED-based trials—"The next time you come to the ER for treatment of abdominal pain, do you want to receive the same medication again?" Patients will be asked to choose among the following responses: "Yes," "No," or "Not sure"
- 3) Side effects. We will use the following question: "Did you have any new symptoms that began only after you got the study medication?" An affirmative response will be followed by an open-ended question eliciting details.

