## IV lidocaine v. hydromorphone for acute abdominal pain. A randomized trial. Version date 07112018

administration

- 3) Patient preference for the medication they received.
- 4) Need for medication to treat associated symptoms such as anti-nausea medication or an anti-histamine

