### Analysis.

Baseline characteristics will be reported as mean (SD), median (IQR), or n/N (%), as appropriate. The primary outcome, improvement in 0-10 pain score between baseline and one hour will be reported as mean (95%CI) for each group. The between-group difference in mean improvement in 0-10 pain score will be calculated with 95%CI. If this 95%CI does not cross zero, the results will be considered statistically significantly different. All dichotomous values will be reported as proportions with 95%CI. For formal statistical testing, we will use the ttest.

We will use an intention to treat analysis. Once an investigational medication is initiated, the patient will be included in the analysis, regardless of whether or not the patient completed the medication infusion and regardless of whether or not the patient requests off-protocol analgesic medication.

**Data collection and processing.** Data acquisition will be performed using REDCap (Research Electronic Data Capture), a secure, web-based application designed specifically to support data capture for research studies. The REDCap project (<http://project-redcap.org/>) is an international project, with more than 70 institutional partners from CTSA and GCRC funded institutions. Paper consent documents will be maintained in locked research cabinets.

**Data monitoring committee and interim analysis.** This committee will be headed by [name], PhD, an epidemiologist and include [name], MD, the director of the Moses ED. The committee will meet every month with the PI to 1) monitor adverse events and develop strategies to minimize these; and, 2) monitor recruitment and enrollment. Because our goal is to report the results with sufficient precision to influence clinical practice, we will not perform an interim efficacy analysis.

**Registration.** The study will be registered at <http://www.clinicaltrials.gov>.

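### Does the plan need a rule for Not sure answers on medication preference, and a named between-arm measure for its yes/no outcomes?

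*Combined protocol and SAP*

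**What the plan says.** The Measures section (item 2) describes the preference question, which asks whether the patient would want the same drug at a future visit for abdominal pain. "Patients will be asked to choose among the following responses", it says, and lists three: Yes, No and Not sure. The same item gives the outcome some weight: "Preference for a specific medication is a highly patient centered outcome". Item 3 of the secondary efficacy outcomes is "Patient preference for the medication they received".

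The Analysis section has two outcome rules and one sentence on testing. For the pain score, "The between-group difference in mean improvement in 0-10 pain score will be calculated with 95%CI". For two-category outcomes, and then for testing in general, "All dichotomous values will be reported as proportions with 95%CI. For formal statistical testing, we will use the ttest". The sentence on testing is not limited to any type of outcome.

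The aim at the end of the Background section is comparative: "To determine the relative efficacy and safety of IV lidocaine among patients with acute abdominal pain", against hydromorphone. All four safety endpoints are defined as frequencies.

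**The concern.** Two things appear to be missing.

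1. **Preference.** A three-category answer is neither a mean nor a two-category value, and a t-test cannot be run on it until Not sure is given a code. No section gives one. If the coding were chosen after the data were seen, the choice could decide whether the result is called significant.
2. **Between-arm measure.** Sufficient relief, need for medication for associated symptoms, and the safety endpoints get a proportion and interval in each arm. No risk difference or ratio is named, although the aim is about relative efficacy and safety.

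At stake are the reading of one secondary outcome and the way the safety comparison is presented. The concern is not that a t-test is invalid on 0/1 data. At this sample size it agrees closely with a chi-square test.

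**Working it through.** **The plan's own figure.** Inputs from the sample size section: difference 1.3, SD 2.8, alpha 0.05 (taken as two-sided), power 0.80.

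n per group = 2 × (1.960 + 0.842)² × 2.8² / 1.3² = 2 × 7.85 × 7.84 / 1.69 = 72.8, so 73. Enrolment is 146 × 1.05 = 153.3, so 154, or 77 per arm. The stated figures reproduce, and nothing in this point touches them.

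**Worked example.** The counts are assumed, because the documents give no preference rates. There are 77 patients per arm and no missing answers. Yes/No/Not sure is 46/12/19 in one arm and 38/24/15 in the other. Each p-value is from a pooled t-test on 0/1 data, and each interval is a Newcombe 95% CI.

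| Coding | Proportions | Difference (95% CI) | p |
|---|---|---|---|
| A: Yes v (No or Not sure) | 46/77 = 59.7% v 38/77 = 49.4% | 10.4 points (-5.2 to 25.3) | 0.198 |
| B: Yes v No, Not sure excluded | 46/58 = 79.3% v 38/62 = 61.3% | 18.0 points (1.6 to 33.1) | 0.031 |
| C: No v (Yes or Not sure) | 12/77 = 15.6% v 24/77 = 31.2% | -15.6 points | 0.022 |

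All three codings favour the first arm. The intervals for A and B share the range from 1.6 to 25.3 points. What moves is the side of 0.05 on which the p-value falls.

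**How often codings differ.** Multinomial simulation, 77 per arm, 100,000 trials per setting, assumed true Yes of 65% v 50%.

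| Not sure (arm 1 / arm 2) | A and B disagree on significance | A and C disagree on significance |
|---|---|---|
| 10% / 10% | 14% | 21% |
| 15% / 15% | 19% | 26% |
| 20% / 20% | 25% | 31% |
| 10% / 20% | 26% | 37% |

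Two facts put these rates in proportion. Coding A has only about 46% power at 65% v 50%, so many trials lie close to the threshold and a small recoding tips them. The codings also estimate different quantities. With Not sure at 10% in both arms, the true difference is 65 - 50 = 15 points under A and 65/0.9 - 50/0.9 = 72.2 - 55.6 = 16.7 points under B. In none of the four settings were A and B both significant in opposite directions.

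**No true difference.** With Yes from 30% to 80% and Not sure from 5% to 30%, each single coding rejects in 4.1% to 5.3% of trials. The chance that at least one of the three is significant is 6.5% to 9.7%. That excess arises only if an analyst tries all three codings and reports the best.

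**Between-arm measure.** With a planned proportion in each arm, the difference is p1 - p2 and its approximate 95% half-width is 1.96 × √(2p(1-p)/77) when both arms share rate p. That is 9.5 points at p = 10%, 14.5 at 30% or 70%, and 15.8 at 50%. Nothing is needed beyond the planned proportions and the arm sizes. If an endpoint such as naloxone has no events in either arm, the t-test is undefined, but the planned per-arm interval still informs: its exact upper limit is 1 - 0.025^(1/77) = 4.7%.

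**The case for a change.** The strongest case for a change is that the Measures section gives preference particular weight, the coding is unwritten, and fixing it would cost one sentence. The intention-to-treat rule does not settle the matter. It says which patients are analysed, not how an answer is coded, and even if it ruled out dropping the Not sure answers, codings A and C would both keep every patient and could still differ. A test is also not an effect estimate, so the sentence on the t-test does not supply a between-arm measure for safety.

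Most of this is factually right: the plan is silent on the coding, and the choice can move a p-value across 0.05. It falls short because the silence leaves little real ambiguity. The outcome is named as preference for the drug received, and the question asks whether the patient wants that drug again, so the event being counted is Yes. That makes it a proportion under "All dichotomous values will be reported as proportions with 95%CI". Coding A is also what one would write down if asked to fill the gap. Nothing in the documents suggests that several codings would be tried and the best one kept, and because the trial is double blind the coding can be settled without knowledge of the arms.

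On the second part, the sentence on testing follows directly after the one on dichotomous values, and its ordinary reading includes them. Restricting the t-test to pain scores would remove the only test named for yes/no outcomes, although that test holds its size on such data.

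**Conclusion.** No change follows. This is a gap in detail that analysts would fill sensibly, and no stated rule gives a wrong result. Preference reads naturally as the proportion answering Yes, and the risk differences come straight from the planned per-arm proportions.

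Under assumed response rates, including or excluding Not sure changes the significance of this one secondary outcome in 14% to 26% of trials. In the worked example it changes neither the direction nor, given the width of the intervals, the broad message. The higher false-positive rate of 6.5% to 9.7% depends on picking the best of three codings, which the documents give no reason to expect.

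The conclusion rests on 77 patients per arm, no missing answers, and preference rates that are assumptions throughout. The primary analysis, the 73 per group and the total of 154 are unaffected.

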## IV lidocaine v. hydromorphone for acute abdominal pain. A randomized trial. Version date 07112018

Consent. Informed consent will be obtained after the patient has been evaluated in the ED, while they are having acute pain. Unfortunately, there is no other feasible way to obtain consent because severe acute abdominal pain is not predictable. As part of this consent process, we will be sure that patients understand they do not have to participate in the study to obtain analgesics. Also, we will offer to help patients call a family member or friend to discuss the study with them if they wish. Finally, we will have the patient's attending physician confirm that the patient has the capacity to consent to participate in the study at the time they are asked to provide consent. Both research associates and health care providers will participate in the consent process. Both will document their participation with a note in Epic and by signing the consent document.

Pyxis procedures. The healthcare provider will place an order in Epic for the study medication. The order will trigger a specific pocket in Pyxis to open. The research associate and the clinical nurse will then complete the RA/RN checklist (Appendix).

Description of orientation and education that providers receive about this study and about research procedures. This study in particular and research procedures in general are introduced during faculty meetings and reinforced with emails and Powerpoints. The PI then meets with providers in brief one-on-one sessions to describe these. Finally, the investigators and research associates discuss these during the in-shift briefs.

### Risks/Benefits

Hydromorphone is commonly used in US EDs for treatment of acute abdominal pain. Intravenous lidocaine is an emerging medication for acute severe pain with some data to support its use. Regardless of results, this study will likely have a national impact. Study subjects will benefit by receiving a medication that is likely to improve their pain. In addition to breach of confidentiality, which is unlikely, and inconvenience to the subject, which will undoubtedly occur, it is likely that subjects will experience adverse medication effects. For the most part, these are nuisance events. All the medications can cause drowsiness, which may be functionally impairing. Opioids such as hydromorphone can cause respiratory depression and hypotension. Lidocaine can very rarely cause hemodynamically significant cardiac arrhythmias or seizures.

### Data Storage & Confidentiality

Data will be stored and maintained in REDCap. Data analysis will occur on password-protected computers. Consent documents will be maintained in locked research cabinets. Only study personnel will have access to the data and consent documents.

